1.1 MeSH Headings for Conditions and Interventions Studied

- Cardiomyopathy, Dilated
- Sudden Cardiac Death
- Myocardial Microvascular Dysfunction
- Magnetic Resonance Imaging, Cardiac
- Myocardial Perfusion Imaging
- Stress Perfusion
- Implantable Cardioverter-Defibrillators
- Cardiac Arrest
- Heart Failure
- Heart Transplantation
- Left Ventricular Assist Devices
- Myocardial Fibrosis
- Coronary Artery Disease
- Myocardial Perfusion Reserve

1.2 MeSH Check Tags

- Humans
- Adult
- Middle Aged
- Aged
- Male
- Female
- Prospective Studies
- Cohort Studies
- Multicenter Studies
- Observational Studies

2. Basic Study Information

Item	Content
Study Title	Study on Risk Early Warning of Clinical Prediction Model Based on MultiParameter Stress Perfusion Cardiac Magnetic Resonance in Adverse Prognosis of Dilated Cardiomyopathy
Study Type	Observational, Prospective, Multicenter Cohort Study
Study Design	Prospective observational cohort study; focusing on evaluating the predictive value of myocardial microvascular dysfunction (MVD) assessed by stress perfusion cardiac magnetic resonance (CMR) for SCD-related events (primary endpoint) and secondary endpoint events in patients with DCM; artificial intelligence (AI) will be briefly used for auxiliary analysis of CMR image features without detailed model development and validation procedures.
Sample Size	Planned enrollment of ≥ 450 patients with DCM (recruited from three study centers) to ensure sufficient statistical power for analyzing the correlation between MVD and SCD-related events.
Study Duration	Total study duration: 36 months (3 months of

	preparation, 9 months of recruitment and baseline assessment, 24 months of follow-up, 6 months of data analysis and report writing)
Follow-up Period	24 months after baseline stress perfusion CMR examination; additional 6 months of follow-up after the occurrence of the primary endpoint event; scheduled follow-up time points: 3 months, 6 months, 12 months, 18 months, 24 months post-CMR, and 1 year, 3 years, 5 years post-CMR for long-term outcome observation.
Primary Endpoint	A composite of SCD-related events, encompassing sudden cardiac death (SCD), appropriate implantable cardioverter-defibrillator (ICD) shock, and resuscitated cardiac arrest (see Appendix S1 for detailed diagnostic criteria) .
Secondary Endpoint	A composite of heart failure–related death, heart transplant, and left ventricle (LV) assist device implantation. Detailed definitions: heart failure-related death refers to death associated with clinically worsening heart failure symptoms without evidence of other causes; LV assist device implantation follows FDA-approved indications for mechanical circulatory support in severe heart failure patients .

Registration Information	Planned to be registered on ClinicalTrials.gov (NCT number to be assigned)
Study Centers	Shandong Provincial Hospital, Jinan Central Hospital, Beijing Anzhen Hospital ; all centers are tertiary grade A hospitals with qualified 3.0T CMR equipment, standardized stress perfusion scanning protocols, and experienced cardiology and radiology teams to ensure the accuracy and consistency of MVD assessment.

3. Research Background and Significance

Dilated cardiomyopathy (DCM) is a common non-ischemic cardiomyopathy characterized by left ventricular or biventricular dilation and reduced systolic function, which is a major cause of sudden cardiac death (SCD) and heart failure in adults. The clinical prognosis of DCM is highly heterogeneous, and identifying patients at high risk of SCD-related events remains a critical clinical challenge, as traditional risk stratification tools have limited predictive efficacy.

Myocardial microvascular dysfunction (MVD), defined as structural and functional abnormalities of the coronary microcirculation (pre-arterioles and intramyocardial arterioles) without significant epicardial coronary artery stenosis, has been increasingly recognized as an important pathological feature of DCM. Previous studies have shown that DCM patients often exhibit impaired myocardial perfusion reserve (MPR), a key indicator of MVD, which is closely associated with the severity of left ventricular dysfunction and myocardial fibrosis. Stress perfusion cardiac magnetic resonance (CMR) is a non-invasive, high-resolution imaging technique that can accurately assess myocardial perfusion reserve and quantify MVD by measuring stress and rest myocardial blood flow (MBF), with good correlation with invasive microvascular function assessment indicators such as index of microvascular resistance (IMR).

Notably, MVD may contribute to the pathogenesis of DCM through stress-induced repetitive myocardial stunning and is closely related to adverse cardiac outcomes, including SCD. However, the predictive value of MVD assessed by stress perfusion CMR for SCD-related events in DCM patients has not been fully clarified, especially in a multicenter setting. Late gadolinium enhancement (LGE) imaging is crucial for distinguishing ischemic from non-ischemic etiologies, as infarct patterns of LGE are indicative of myocardial ischemia, which needs to be excluded in DCM studies to ensure etiological purity and avoid confounding effects on MVD assessment.

Conducted in three renowned tertiary hospitals (Shandong Provincial Hospital, Jinan Central Hospital, Beijing Anzhen Hospital), this study aims to explore the correlation between MVD (assessed by stress perfusion CMR) and SCD-related events in DCM patients, clarify the predictive value of MVD for the primary endpoint, and provide a scientific basis for individualized risk stratification and early warning of SCD in DCM patients. Artificial intelligence (AI) will be briefly used for auxiliary extraction of CMR image features to improve the efficiency of image analysis, without in-depth development and validation of AI prediction models.

4. Research Objectives

4.1 Primary Objective

To evaluate the predictive value of myocardial microvascular dysfunction (MVD) assessed by stress perfusion CMR for SCD-related events (SCD, appropriate ICD shock, resuscitated cardiac arrest) in DCM patients, and confirm whether MVD is an independent risk factor for the primary endpoint.

4.2 Secondary Objectives

- To analyze the correlation between MVD severity (assessed by stress perfusion CMR indicators) and the occurrence of secondary endpoint events (heart failure-related death, heart transplant, LV assist device implantation).
- To explore the relationship between MVD and other DCM-related indicators (left ventricular structure and function, myocardial fibrosis, laboratory indicators such as NT-proBNP), and clarify the potential mechanism of MVD in predicting SCD-related events.
- To briefly apply AI technology for auxiliary extraction of stress perfusion CMR image features, improving the efficiency and consistency of MVD assessment.
- To establish a standardized method for MVD assessment using stress perfusion CMR in DCM patients, providing a reference for clinical practice.

5. Study Subjects and Inclusion/Exclusion Criteria

5.1 Inclusion Criteria

1. A diagnosis of DCM confirmed using the World Health Organization/International Society and Federation of Cardiology (WHO/ISFC) criteria. The diagnosis is based on an elevated left ventricular end-diastolic volume indexed to body surface area (LVEDV/BSA) and reduced left ventricular ejection fraction (LVEF), compared with published age- and gender-specific reference values. Reference values for LVEDV/BSA and LVEF are adopted from internationally recognized guidelines to ensure diagnostic consistency.
2. Age >18 years, regardless of gender.

3. During the study period, were seen in the Cardiology Department of Shandong Provincial Hospital, Jinan Central Hospital, or Beijing Anzhen Hospital, or referred for stress perfusion CMR assessment.
4. Able to understand and sign the informed consent form voluntarily, and can complete the scheduled follow-up.
5. Complete clinical data (including medical history, physical examination, laboratory tests, electrocardiogram, etc.) are available.

5.2 Exclusion Criteria

1. Presence of significant coronary artery disease (CAD), defined as a stenosis of $>50\%$ in a major coronary artery. For left main coronary artery stenosis, a threshold of $\geq 50\%$ is also considered significant, consistent with clinical diagnostic criteria for CAD, to exclude the impact of epicardial coronary stenosis on MVD assessment.
2. Infiltrative diseases (e.g., cardiac amyloidosis, sarcoidosis) that may affect myocardial structure and function and mimic DCM, as these diseases may independently cause MVD and confound the study results.
3. Valvular cardiomyopathy, which may cause ventricular dilation and systolic dysfunction similar to DCM, and may be associated with secondary MVD.
4. Presence of infarct patterns of LGE on CMR imaging. Infarct patterns of LGE are defined as subendocardial enhancement corresponding to a coronary artery territory, which is characteristic of ischemic myocardial injury; exclusion of such patients ensures that those with ischemic etiologies are not included in the study, avoiding interference with the assessment of MVD in non-ischemic DCM.
5. Active malignant tumors, severe systemic infections, or other diseases that may affect the study results and prognosis.
6. Contraindications to CMR examination (such as pacemaker implantation, non-removable metal implants, severe claustrophobia, allergy to gadolinium contrast agent, etc.) or contraindications to stress perfusion (such as severe hypotension, severe asthma, hypersensitivity to adenosine).
7. Previous heart transplantation or left ventricular assist device (LVAD) implantation.
8. Pregnant or lactating women (confirmed by pregnancy test).
9. Unable to cooperate with CMR examination, follow-up, or data collection due to mental illness, cognitive impairment, or other reasons.
10. Participating in other clinical trials that may affect the results of this study.

5.3 Exclusion Criteria After Enrollment (Withdrawal Criteria)

1. Found to not meet the inclusion criteria or meet any of the exclusion criteria after enrollment.

2. Lost to follow-up (no contact for more than 3 months, or failed to complete the scheduled follow-up without reasonable reasons).
3. Voluntarily requests to withdraw from the study (the right to withdraw at any time without affecting subsequent medical treatment).
4. Occurrence of severe adverse events that make it impossible to continue participating in the study.
5. Violation of the study protocol (such as refusing to complete CMR re-examination, providing false information, etc.).

6. Study Process

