6.3 Follow-up

1. **Follow-up Frequency and Time Points:** Follow-up will be conducted at 3 months, 6 months, 12 months, 18 months, and 24 months after baseline stress perfusion CMR examination. For subjects who experience the primary or secondary endpoint event, additional follow-up will be conducted for 6 months to record the recovery and long-term prognosis after the event. In addition, long-term follow-up will be conducted at 1 year, 3 years, and 5 years post-CMR to observe long-term outcomes.
2. **Follow-up Methods:** A combination of outpatient follow-up, telephone follow-up, and medical record review will be used. At each follow-up, researchers will record the occurrence of endpoint events (in detail for SCD-related events and secondary endpoint events), changes in clinical symptoms, medication adjustments, re-examination results (NT-proBNP, electrocardiogram, and CMR re-examination if necessary), and adverse events. For subjects with MVD at baseline, changes in MVD severity will be assessed by stress perfusion CMR re-examination at 12 and 24 months if clinically feasible.
3. **Endpoint Event Judgment:** An endpoint event judgment committee composed of 3 senior cardiologists will be established to review and confirm the occurrence of endpoint events. The committee will make a judgment based on medical records, examination results, and follow-up records, referring to the diagnostic criteria in Appendix S1 for SCD-related events, to ensure the accuracy and objectivity of the data. For SCD, the definition is death due to cardiac causes occurring within 1 hour of symptom onset with sudden loss of consciousness; for

appropriate ICD shock, it refers to shocks delivered in response to hemodynamically unstable ventricular tachycardia or fibrillation without reversible causes ; for resuscitated cardiac arrest, it refers to a cardiac arrest event reversed by cardiopulmonary resuscitation, defibrillation, or pacing .

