Statistical analysis will be performed using SPSS 26.0 and R software (version 4.2.0). Measurement data will be expressed as mean \pm standard deviation (SD) if normally distributed, or median (interquartile range, IQR) if abnormally distributed; comparison between groups will be performed using t-test, non-parametric test (Mann-Whitney U test, Kruskal-Wallis test) as appropriate. Count data will be expressed as rate (%) and compared using χ^2 test or Fisher's exact test. The Kaplan-Meier method will be used to draw the survival curve of subjects (for endpoint events), and the log-rank test will be used to compare the event rate between DCM patients with and without MVD. Multivariate Cox proportional hazards regression model will be used to screen the independent risk factors for SCD-related events and secondary endpoint events, with MVD (assessed by stress perfusion CMR) as the key independent variable. The receiver operating characteristic (ROC) curve will be used to evaluate the predictive efficacy of MVD for SCD-related events, and the AUC value will be calculated. $P < 0.05$ will be considered statistically significant. Subgroup analysis will be performed based on age, gender, LVEF, and MVD severity to explore the predictive value of MVD in different subgroups.

11. Study Schedule

Study Stage	Time Arrangement (Months)	Key Tasks
Preparation Stage	1–3	Finalize the study protocol, train researchers and related personnel (focusing on stress perfusion CMR scanning and MVD assessment), standardize CMR scanning parameters, establish the data management system, design Appendix S1 (diagnostic criteria for SCD-related events), and obtain ethical approval from each research center.

Recruitment and Baseline Assessment Stage	4–12	Recruit subjects, conduct baseline assessment (clinical data collection, laboratory tests, electrocardiogram, stress perfusion CMR examination), review inclusion/exclusion criteria, assess MVD using stress perfusion CMR (with brief AI auxiliary analysis), and complete data entry and verification.
Follow-up Stage	13–36	Conduct regular follow-up, record endpoint events and adverse events, perform stress perfusion CMR re-examination at 12 and 24 months (if feasible) to assess changes in MVD severity, update study data, and conduct long-term follow-up at 1 year, 3 years, and 5 years post-CMR.

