Appendix S1: Diagnostic Criteria for SCD-Related Events

1. Sudden Cardiac Death (SCD): Death due to cardiac causes occurring within 1 hour of the onset of acute cardiac symptoms, characterized by sudden loss of consciousness. For unwitnessed deaths with clear evidence of cardiac etiology, it is classified as probable SCD .
2. Appropriate Implantable Cardioverter-Defibrillator (ICD) Shock: Shocks delivered by an ICD in response to hemodynamically unstable ventricular tachycardia (VT) or ventricular fibrillation (VF) that is not caused by reversible factors (such as electrolyte imbalance, drug effects) .
3. Resuscitated Cardiac Arrest: A cardiac arrest event that is reversed, usually by cardiopulmonary resuscitation (CPR), defibrillation, cardioversion, or cardiac pacing, with restoration of spontaneous circulation .

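### The three-month loss-to-follow-up rule conflicts with the protocol's own visit gaps and classes silent patients as lost without a vital-status check, so sudden deaths can be missed

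*Protocol*

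**What the plan says.** Section 5.3 carries the title "5.3 Exclusion Criteria After Enrollment (Withdrawal Criteria)", so meeting any of its items takes a patient out of the study. Item 2 reads: "Lost to follow-up (no contact for more than 3 months, or failed to complete the scheduled follow-up without reasonable reasons". The three months are not tied to a missed visit, and no contact attempts or status check come before the classification.

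The schedule is in Section 6.3 item 1: "Follow-up will be conducted at 3 months, 6 months, 12 months, 18 months, and 24 months after baseline stress perfusion CMR examination". Beyond that, "long-term follow-up will be conducted at 1 year, 3 years, and 5 years post-CMR to observe long-term outcomes". On method, item 2 of the same section says: "A combination of outpatient follow-up, telephone follow-up, and medical record review will be used".

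The primary endpoint (Section 2) is "A composite of SCD-related events, encompassing sudden cardiac death (SCD), appropriate implantable cardioverter-defibrillator (ICD) shock, and resuscitated cardiac arrest". Appendix S1 adds: "For unwitnessed deaths with clear evidence of cardiac etiology, it is classified as probable SCD".

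Section 9 item 4, under the label of voluntary withdrawal, says that data of subjects who withdraw are kept and analysed unless the subject asks for deletion.

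**The concern.** There are two problems. First, the limit is shorter than most of the gaps that the protocol itself schedules. Three centres could apply it in different ways, and the second limb of the rule (follow-up not completed, without an acceptable reason) has no objective test to settle the matter.

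Second, the rule acts on silence, and in this population silence can be the outcome. A patient who dies suddenly at home stops attending and stops answering. If that patient is classed as lost and nobody is required to find out whether he or she is alive, the death may never reach the endpoint committee. Appendix S1 raises the stakes: an unwitnessed death counts as probable SCD only when there is clear evidence of a cardiac cause, so it must be discovered and documented to count at all.

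At stake are events for the primary analysis and the assumption behind Kaplan-Meier and Cox methods (Section 10) that censoring is unrelated to the event risk.

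**Working it through.** **Inputs.** Limit: more than 3 months without contact (Section 5.3 item 2). Contacts: baseline and months 3, 6, 12, 18 and 24, then years 3 and 5 (Section 6.3 item 1); the 1-year contact coincides with month 12. Enrolment: at least 450 (Section 2). The protocol states no event rate, so it has no figure of its own to reproduce here.

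**Step 1: gaps, to month 24.** Contacts at 0, 3, 6, 12, 18, 24 give gaps of 3, 3, 6, 6 and 6 months. Three of the five exceed the limit.

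**Step 2: literal reading, to month 24.** Time past the limit is the sum of max(0, gap − 3) = 0 + 0 + 3 + 3 + 3 = 9 months, that is months 9–12, 15–18 and 21–24. 9/24 = 37.5%. This assumes no contact outside the scheduled visits.

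**Step 3: literal reading, to year 5.** Contacts at months 36 and 60 add gaps of 12 and 24 months. Time past the limit = 9 + (12 − 3) + (24 − 3) = 9 + 9 + 21 = 39 months. 39/60 = 65%.

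**Step 4: what happens to a silent death.** Take a patient who dies unreported just after the month-6 visit.
- Literal reading: the limit passes just after month 9, about three months before the month-12 contact that could reveal the death.
- Lenient reading (3 months after a missed contact): the month-12 contact is missed and the patient becomes lost at about month 15.

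In neither case does Section 5.3 or Section 6.3 require anyone to establish vital status before the classification.

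**Step 5: does Section 9 item 4 repair this?** If it extends to lost patients, their collected data stay in the analysis and they are censored. That protects recorded events. It does not bring in a death after the last contact, because that death was never recorded.

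**Step 6: illustration only; all rates are assumed.** Suppose 3% of patients per year have a primary event. Over two years the expected number is 450 × (1 − exp(−0.06)) = 26.2. Suppose SCD makes up 30–50% of these and 10–30% of such deaths reach the study only as lost contact. The share missed runs from 0.3 × 0.1 = 3% to 0.5 × 0.3 = 15%, which is 26.2 × 0.03 = 0.8 to 26.2 × 0.15 = 3.9 events, or roughly 1 to 4. None of these three rates comes from the documents. Some of these deaths would stay unknown under any rule.

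**The case against.** The strongest reply is that nobody would read the rule literally. In ordinary use, a patient is lost when he or she cannot be reached, not when no contact was due, and unscheduled contact is not ruled out. This has force: the 9-of-24-months figure shows a defect of wording, and does not predict that sites will withdraw adherent patients. But the lenient meaning has to be supplied by the reader, and it leaves the second problem in place.

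The second reply is that deaths can still be found. Telephone follow-up is not limited to the patient, record review may continue, and a three-cardiologist committee judges events. All true. Yet the committee sees only what is brought to it, and no tracing is required before a patient is classed as lost.

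Three stronger readings are tempting and are not supported:
- A reader might infer that lost patients, or events already recorded, are deleted. Section 9 item 4 points the other way, although its reach to lost patients is unclear.
- A reader might infer that loss differs by MVD status, because only patients with baseline MVD have planned re-scans. Those fall at months 12 and 24, when every patient already has a visit, so they add no scheduled contact date. No direction of bias in the hazard ratio follows.
- A reader might infer from Section 11, where the follow-up stage opens at month 13, that early visits are skipped. Section 6.3 ties visits to each patient's own CMR date, and the stage label has no bearing on the loss rule.

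**Conclusion.** The point holds in this form: the protocol fixes a loss rule that conflicts with its own schedule and that, on either reading, classes silent patients as lost without establishing whether they are alive. The conflict is arithmetic on the protocol's own figures: 9 of 24 months past the limit on a literal reading with scheduled contacts only.

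The likely harm is missed primary events and informative censoring, not deletion of patients or of recorded events. Its size and direction cannot be computed from the documents. The 1 to 4 events out of about 26 are an illustration under assumed rates and carry no more weight than those assumptions. This is not a detail that can wait for an analysis plan, because the protocol itself states the rule and a death not traced in time may not be recoverable later.

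**What to change.** 1. Reconcile Section 5.3 item 2 with the Section 6.3 schedule, so that the clock starts at a missed scheduled contact.
2. Define loss by unknown status: a patient is lost only if vital status and endpoint status both remain unknown after a missed scheduled contact and documented attempts through the patient, family, treating hospital and available death records.
3. Record a missed visit as a missed visit. It should not withdraw the patient.
4. Extend Section 9 item 4 expressly to patients lost to follow-up: they stay in the analysis, censored at the last date known to be alive and event-free.

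The cost is a change of wording plus a few extra calls and record checks for silent patients. It needs no additional patients and no change to the visit schedule.

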Subsequent large-scale development, optimization, and independent validation of artificial intelligence models will be performed in this study. The primary objective remains the evaluation of the predictive value of MVD, as assessed by stress perfusion CMR, for sudden cardiac death (SCD) – related adverse events.

8. Quality Control

1. **Personnel Training:** Before the start of the study, all researchers, radiologists, data managers, and study coordinators will receive unified training on the study protocol, SOP, data collection requirements, endpoint event judgment criteria, stress perfusion CMR scanning and MVD assessment standards, and ethical norms to ensure the consistency of operation.
2. **CMR Quality Control:** All research centers will use 3.0T magnetic resonance scanners of the same model, and the scanning parameters (including stress perfusion sequences) will be standardized. A professional CMR quality control team will regularly check the image quality (once every 3 months); unqualified images will be re-scanned if necessary, and subjects who cannot complete the stress perfusion CMR examination will be excluded from the study. The consistency of MVD assessment by radiologists will be tested using Kappa analysis, with Kappa value ≥ 0.80 required to ensure reliability.
3. **Data Quality Control:** The data management team will conduct regular inspections of the CRF data, with special focus on MVD-related indicators and endpoint event records, and any problems found will be fed back to the researchers in a timely manner for correction. The final data will be locked after verification to prevent data tampering. A random sample of 10% of the CRF data will be reviewed by the study leader to ensure data quality.
4. **Ethical Supervision:** The Ethics Committee of each research center will supervise the entire study process, review the study protocol and informed consent form regularly, and handle adverse events and ethical issues in a timely manner to ensure that the study is carried out in accordance with ethical principles.

9. Ethical Considerations

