1. **Informed Consent:** All subjects will sign the informed consent form voluntarily after fully understanding the purpose, process, potential risks, and benefits of the study. The informed consent form will be provided in both Chinese and English (if necessary) to ensure that subjects can understand the content. Subjects have the right to ask questions about the study, and researchers will answer truthfully.
2. **Confidentiality of Subject Information:** The personal information of subjects (such as name, ID number, contact information) will be encrypted and stored, and will not be disclosed to any third party. The study data will be used only for scientific research purposes, and the identity of subjects will be anonymized during data analysis.
3. **Risk Management:** During the study, if subjects experience adverse events related to the study (such as contrast agent allergy during CMR examination, hypotension during adenosine infusion for stress perfusion), researchers will take timely and effective medical measures to ensure the safety of subjects. All adverse events will be recorded in detail and reported to the Ethics Committee and the study leader within 24 hours. For subjects with high risk of SCD-related events identified during follow-up (especially those with severe MVD), researchers will promptly inform the treating physician to adjust the treatment plan (e.g., considering ICD implantation).

4. Voluntary Withdrawal: Subjects have the right to withdraw from the study at any time without any reason, and their medical treatment will not be affected. The data of subjects who withdraw from the study will be retained and included in the final data analysis (unless the subject requests to delete the data).

10. Statistical Analysis

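### Refusing a CMR re-examination is a ground for withdrawal, yet the dated re-scans are set mainly for patients with MVD, so the rule can cost outcome follow-up predominantly in the exposed group

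*Protocol*

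**What the plan says.** Protocol section 5.3 lists reasons for removing a patient after enrolment. Item 5 reads "Violation of the study protocol (such as refusing to complete CMR re-examination, providing false information, etc".

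Who is asked for a re-scan is described in several places:

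- Section 6.3 item 2: "For subjects with MVD at baseline, changes in MVD severity will be assessed by stress perfusion CMR re-examination at 12 and 24 months", qualified by clinical feasibility.
- The same item, for follow-up visits of any patient: "re-examination results (NT-proBNP, electrocardiogram, and CMR re-examination if necessary), and adverse events".
- Section 11, schedule table: "perform stress perfusion CMR re-examination at 12 and 24 months (if feasible) to assess changes in MVD severity", with no restriction to patients with MVD.
- Section 8 item 2, on image quality, for any patient: "unqualified images will be re-scanned if necessary".

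On the data of withdrawn patients, section 9 item 4 (Voluntary Withdrawal) says "The data of subjects who withdraw from the study will be retained and included in the final data analysis", unless the patient asks for deletion. No section says whether endpoint follow-up continues after a withdrawal under section 5.3 item 5.

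The main comparison is in section 10: "the log-rank test will be used to compare the event rate between DCM patients with and without MVD", together with a Cox model in which MVD is the key variable. Under section 6.3, endpoints are gathered from clinic visits, telephone contact and medical records, and a committee then adjudicates them.

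**The concern.** Baseline MVD is the exposure. It also largely decides who is routinely asked for the procedure whose refusal ends participation. A patient without MVD normally has no dated re-scan to refuse.

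The repeat scan serves the assessment of change in MVD. It is not needed to establish sudden death, an appropriate ICD shock, a resuscitated arrest or any component of the secondary endpoint. The rule therefore gives up primary-outcome data over a procedure that the primary outcome does not depend on.

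Two things are at stake. Events are lost, mainly from the MVD group. In addition, Kaplan-Meier, log-rank and Cox methods all assume that censoring is unrelated to risk within groups. Willingness to undergo a second adenosine stress scan may be related to prognosis; if it is, the hazard ratio is biased. Removal at month 12 would also forfeit the 3- and 5-year outcomes planned in section 6.3.

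**Working it through.** **Text check.** Setting the sections side by side:

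1. Section 5.3 item 5 makes refusal of a re-examination a withdrawal, without limiting it to particular scans.
2. Section 6.3 fixes re-scans in time only for patients with baseline MVD. Everyone else is re-scanned only on need.
3. The section 11 table repeats the two time points without the MVD restriction, so sections 6.3 and 11 do not agree.
4. Section 9 item 4 concerns voluntary withdrawal. Even if it extends to item 5, it keeps data already collected; it does not provide for further follow-up.

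Taking section 6.3 as the specific instruction, exposure to the rule is concentrated in the MVD group.

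**Scale.** The protocol states no figure that this point disputes. It gives at least 450 patients and 24 months of follow-up, but no MVD prevalence, event rate, effect size or refusal rate. Everything below other than 450 and 24 is assumed: half have MVD (225), true hazard ratio 2.0, a fraction r of MVD patients refuse at month 12 and are censored there, and refusers have k times the hazard of other MVD patients.

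Ignoring depletion by events, the observed 24-month hazard ratio is

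HR = 2.0 × A / B, with A = [24(1−r) + 12rk] / [24(1−r) + 12r] and B = (1−r) + rk.

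A is the average hazard over the person-time kept, and B the average over all MVD patients, both relative to non-refusers.

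| r | k | A | B | HR |
|---|---|---|---|---|
| 0.10 | 1.5 | 23.4/22.8 = 1.0263 | 1.05 | 1.955 |
| 0.20 | 2 | 24.0/21.6 = 1.1111 | 1.20 | 1.852 |
| 0.20 | 3 | 26.4/21.6 = 1.2222 | 1.40 | 1.746 |
| 0.10 | 0.5 | 22.2/22.8 = 0.9737 | 0.95 | 2.050 |
| 0.20 | 0.5 | 20.4/21.6 = 0.9444 | 0.90 | 2.099 |
| any | 1 | 1 | 1 | 2.000 |

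Allowing for depletion, with exponential event times and an assumed 24-month risk without MVD of 4% or 8%, moves these values by less than 0.01.

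**Events lost when refusal is unrelated to risk.** Refusers number 225 × 0.10 = 22.5 to 225 × 0.20 = 45. With 8% risk without MVD and hazard ratio 2.0, an MVD patient is event-free at month 12 with probability 0.92 and at month 24 with probability 0.92² = 0.8464.

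- r = 0.20, 8% risk: 45 × (0.92 − 0.8464) = 3.3 events lost, of 225 × 0.08 + 225 × 0.1536 = 52.6.
- r = 0.20, 4% risk: 45 × (0.96 − 0.9216) = 1.7 events lost, of 225 × 0.04 + 225 × 0.0784 = 26.6.

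At r = 0.10 the losses are half of these. In this illustration all come from the MVD group.

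**The case against.** The strongest reply has four parts.

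- **The rule is not confined to patients with MVD.** This stands. Item 5 covers any re-examination, section 6.3 allows one for anybody if needed, section 8 allows quality re-scans, and the section 11 table carries no MVD restriction. A reader might infer that only the exposed group can be removed; the text supports predominantly, not solely. If the section 11 wording governs, much of the asymmetry disappears. What remains is a rule that ties outcome follow-up to a scan the outcome does not need, and two sections that disagree.
- **Loss of follow-up is inferred.** This stands as a qualification. It is the natural reading of withdrawal, but it is not stated. A reader might go further and infer that withdrawn patients are deleted from the analysis. The documents do not say so, and the retention sentence in section 9 points the other way, although it sits under voluntary withdrawal.
- **Patients too unwell for the scan are already covered.** This largely stands. The re-scan is conditional on feasibility, and an infeasible scan is not a refusal. The concern is with patients who could be scanned but decline, and the protocol does not say where the line falls.
- **Withdrawal handling belongs in the analysis plan.** This does not stand for data collection. An analysis plan can define populations, but it cannot recover follow-up that the protocol stopped.

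**Conclusion.** The point holds in a limited form. The withdrawal rule falls predominantly on the MVD group, and on its natural reading it stops endpoint follow-up for a reason unconnected with the endpoint.

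Under the assumptions shown, the 24-month hazard ratio moves from 2.0 to about 1.96–1.75 (2% to 13% lower) if refusers are at higher risk, and to about 2.05–2.10 (2.5% to 5% higher) if they have half the risk. These figures give scale only, because refusal rate, MVD prevalence and refuser risk are all unknown.

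Two stronger conclusions are tempting and not supported. The first is that bias is inevitable: if refusal is unrelated to risk the hazard ratio stays at 2.0, and only events and precision are lost. The second is a larger distortion obtained from the second year alone, 2.0/1.05 = 1.90 to 2.0/1.40 = 1.43. The protocol plans no year-2 analysis, and first-year events are unaffected by a refusal at month 12. A refusal at month 24 costs no 24-month follow-up, though it could cost the later outcomes.

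**What to change.** 1. In section 5.3 item 5, delete the reference to refusing CMR re-examination.
2. State that a refused, infeasible or missed re-scan is missing data for the MVD-change assessment only. The patient stays in endpoint follow-up on the common schedule, grouped by the baseline MVD result, unless consent to follow-up is withdrawn.
3. Reconcile sections 5.3, 6.3, 9 and 11 on who is re-scanned, whether endpoint follow-up continues after a withdrawal that is not the patient's own request, and whether the retention sentence in section 9 item 4 covers such withdrawals.

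The cost is a short amendment touching four sections. It adds no scans and no new type of visit: patients who would have been removed simply complete the contacts already planned. It should be made before the first month-12 re-scans, because outcome data not collected cannot be restored by analysis.
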